14.6. APPENDIX 6 - ACCEPTABLE TIME WINDOWS FOR ASSESSMENTS/ PROCEDURES

Assessment/Procedure	Window
Infusion Bag 1 begins approximately 2 hrs prior to reperfusion	> 1 hour prior to reperfusion
Change loading dose to maintenance dose @ 30 mins	30-35 minutes after start of infusion
Change Infusion Bag 1 to Infusion Bag 2 @ 24 hrs after start of infusion	± 1 hour
End of Infusion @ 48 hrs	± 1 hour
PaO ₂ /FiO ₂ ratio measurements	
@ ICU Admission	± 2 hour
@ 24 hrs	± 2 hour
@ 48 hrs	± 4 hours
@ 72 hrs	± 4 hours
X-ray to calculate PGD Score	
@ ICU Admission	± 4 hour
@ 24 hrs	± 4 hours
@ 48 hrs	± 8 hours
@ 72 hrs	± 8 hours
Vitals & Cardiopulmonary measurements @ ICU admission and every 12 hours after ICU admission for 5 days or ICU discharge (whichever occurs earlier)	± 4 hours
Renal & Hepatic Function after infusion start	
@ 12 hrs	± 4 hours
@ 24 hrs	± 4 hours
@ 36 hrs	± 4 hours
PK samples	
After infusion start	24 ± 6 hours
Just prior to end of infusion	Up to 1 hour prior to infusion end
Post infusion end	2-6 hours
Mechanical Ventilation/Discharge	
@ 8 am every morning	± 4 hours
Hospital discharge blood sample	Up to 24 hours prior to discharge
Month 1 visit post transplant	30-35 days
Month 6 & Month 12 visits	± 2 weeks

**GLOSSARY OF ABBREVIATIONS**

AE	Adverse Event
ALT	Alanine Aminotransferase
APTT	Activated Partial Thromboplastin Time
AST	Aspartate Aminotransferase
ATC	Anatomic Therapeutic Chemical Classification
BAL	Bronchoalveolar Lavage
BOS	Bronchiolitis Obliterans Syndrome
BP	Blood Pressure
CMV	Cytomegalovirus
CO	Cardiac Output
CRF	Case Report Form
CSR	Clinical Study Report
CVP	Right Atrial Pressure
CXCL8	CXC ligand 8 [formerly interleukin (IL)-8]
DMC	Data Monitoring Committee
Dompé	Dompé pha.r.ma s.p.a
FEV 1	Forced Expiratory Volume in One Second
FiO 2	Fraction of Inspired Oxygen
FVC	Forced Vital Capacity
HR	Heart Rate
i.v.	Intravenous
ICU	Intensive Care Unit
ITT	Intention-To-Treat
mmHg	Millimeters mercury
PPD	PPD
PA	Pulmonary Artery
PaO 2	Partial Pressure of Arterial Oxygen
PCWP	Partial Capillary Wedge Pressure
PGD	Primary Graft Dysfunction
PK	Pharmacokinetic
PMN	Polymorphonuclear Leukocyte
PP	Per Protocol
PT	Prothrombin Time
PVR	Pulmonary Vascular Resistance
SAP	Statistical Analysis Plan
SAE	Serious Adverse Event
SOC	System Organ Class
SVR	Systemic Vascular Resistance

## 1 INTRODUCTION

### 1.1 General

This statistical analysis plan (SAP) describes the statistical methods to be used during the analysis and reporting of data collected under Dompé pha.r.ma s.p.a. (Dompé) Protocol REP0104.

The study is split into two phases: screening to one month post-transplant and greater than one month to 12 months post-transplant. This SAP applies to all outputs, in-text or post-text, produced for inclusion in the clinical study report (CSR) for the Month 1 analyses. A separate SAP will be produced for the Month 12 analyses. This SAP should be read in conjunction with the study protocol and case report form (CRF). This version of the plan has been developed using the revised protocol dated 30 August 2005; the CRF dated 01 March 2005 and the amended pages relating to the 30 August protocol amendment. Any further changes to the protocol or CRF may necessitate updates to the SAP.

At the time of writing this version of the SAP, approximately 60 patients have been randomized into the study.

The analysis plan will be finalized and approved by the sponsor and PPD prior to database lock.

### 1.2 Changes from Protocol

None.

### 1.3 Changes from previous versions of SAP

For the primary analysis, the covariance matrix for the final model was wrongly defined as the matrix with the highest value for the Akaike's Information Criterion. The selection criterion has been changed to the matrix with the lowest value for the Akaike's Information Criterion.

## 2 STUDY OBJECTIVES

To evaluate whether CXCL8 inhibition with repertaxin leads to reduced severity of primary graft dysfunction (PGD), as the result of improved functional and clinical outcomes in lung transplantation patients.

The safety of repertaxin in the specific clinical setting will also be evaluated.

The ability of repertaxin to reduce target cells (PMN) infiltration into the graft will be evaluated to confirm its mechanism of action. Plasma levels of repertaxin and its major metabolite will be measured at steady state conditions to provide population pharmacokinetic (PK) profile in this clinical setting.

## 3 STUDY DESIGN

### 3.1 Overview

This is a phase 2, multi-center, randomized, double blind, placebo-controlled, parallel group study of repertaxin in the prevention of PGD after lung transplantation. The study will involve 100

patients undergoing single or bilateral lung transplant who will be randomized to receive either repertaxin or placebo via continuous intravenous (i.v.) infusion administered over 48 hours. Patients randomized into the study who do not go on to receive study drug or lung transplant will be replaced therefore the total number of patients randomized may exceed 100. Patients will be followed for 12 months post-transplant but the majority of study assessments are performed during the intensive care unit (ICU) and hospital stay immediately after surgery.

Patients will be selected for entry into the study from those listed on the center's lung transplant waiting list. Inclusion/exclusion criteria (as listed in protocol sections 5.1 and 5.2), disease history, extrapulmonary site of infection, significant medical history, vital signs, renal and hepatic function, laboratory safety tests and donor information will all be assessed prior to randomization to ensure patient eligibility.

The lung transplant surgery will be performed according to the center's standard practice. The study drug infusion will start approximately 2 hours before the anticipated time of reperfusion of the first allograft. A loading dose will be administered for the first 30 minutes, followed by a maintenance dose for the remaining 47.5 hours of administration.

After completion of surgery, patients will be admitted to an ICU and blood gases ( $\text{PaO}_2$ ,  $\text{FiO}_2$  and  $\text{PaO}_2/\text{FiO}_2$  ratio) will be measured on admission (time 0) and at 24, 48 and 72 hours post ICU admission or until extubation whichever occurs earlier. Chest x-rays, renal and hepatic function and PK sampling will be measured at defined time points within the 72 hours following ICU admission. Vital signs (BP and HR) and cardiopulmonary measurements will be assessed at defined time points within the 5 days post ICU admission or until ICU discharge (or PA catheter removed) whichever occurs earlier. Further patient assessments are made at ICU discharge and hospital discharge.

Patients will return to the center at least 30 days after the transplant for the Month 1 assessment and at 24-28 weeks and 50-54 weeks post transplant for the Month 6 and Month 12 assessments respectively. Once data up to and including the Month 1 assessment has been collected, entered and cleaned, the Month 1 database will be locked, the study will be unblinded and the primary analysis of safety and efficacy data will be performed. Data collected during the open phase of the study i.e. at Months 6 and 12 will be presented in an addendum to the main CSR.

An independent Data Monitoring Committee (DMC) has been established to ensure patient safety, to consider patient risks against the potential for meeting trial objectives, and to provide recommendations to Dompé with respect to the conduct and analysis of the trial. PPD will be responsible for providing the DMC statistician with listings of data relating to disposition (randomization, completion and withdrawal), demography, adverse events (AEs) and occurrence of clinically diagnosed PGD. Full details of the responsibilities of the DMC are provided in the DMC Charter.

### 3.2 Sample Size Considerations

Under the following assumptions:

1. A single primary endpoint –  $\text{PaO}_2/\text{FiO}_2$  ratio
2. One primary comparison: repertaxin versus placebo at 24 hours post ICU admission ( $H_0: \mu_R = \mu_P$ ;  $H_1: \mu_R > \mu_P$ ).
3. A one-sided two group t-test of statistical significance
4.  $\alpha$ -level or probability of Type I error associated with the test of 0.05
5. A placebo mean of 315 mmHg
6. A common standard deviation of 137 mmHg
7. A sample size of 50 in each group

the study has 81% power to detect a difference in means of 70 mmHg ( $\mu_R = 385$  mmHg) and 56% power to detect a difference in means of 50 mmHg ( $\mu_R = 365$  mmHg). The data for assumptions 5 and 6 is taken from the results of 700 lung transplant operations at the Washington University. However, there are currently no data available to provide an estimate of the treatment effect size for this study.

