9. STATISTICAL ISSUES

9.1. SAMPLE SIZE

The sample size has been estimated based on PaO₂/FiO₂ ratios immediately and at 24 hours from the results of 700 lung transplant operations at the Washington University. The database reports means and standard deviations for this endpoint of 329±137 mmHg at the initial ICU assessment and 315±117 mmHg at 24 hours.

A sample size of 50 in each group will have a 81% power to detect a difference in means of 70 mmHg (the difference between a placebo mean of 315 and a treated mean of 385, a 22% improvement) assuming that the common standard deviation is 137 using a two group t-test with a 0.05 one-sided significance level. Alternatively, a sample size of 50 in each group will have a 56% power to detect a difference in means of 50 mmHg (the difference between a placebo mean of 315 and a treated mean of 365, a 15% improvement) assuming that the common standard deviation is 137 using a two group t-test with a 0.05 one-sided significance level.

There is no currently available data to provide a knowledgeable estimate of the effect size in this study. If the effect size is smaller than 15%, the power of this study will be reduced and the chance of a Type II error is increased. Under such circumstances, this study would still provide valuable data regarding the effect size in the primary outcome variable as well as the results in all of the secondary, exploratory endpoints and subgroup analysis.

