#### Primary analysis

The ratio at the two time points will be analyzed using a repeated measurements model using PROC MIXED within SAS®. The model will include fixed effect terms for center, time point and treatment. Time point will be specified as a repeated measurement. In order to select an appropriate matrix for the observations within each patient, 3 models will be fitted using the compound symmetry, Huynh-Feldt and unstructured structures. The matrix for the final model will be selected using Akaike's Information Criterion where the lowest value indicates the best fit. Type III sums of squares from the mixed procedure within SAS® will be used to assess the significance of individual terms within the model using the selected matrix structure. The importance of the treatment-by-center interaction will be investigated but if the term is not significant at the 10% level, it will be excluded from subsequent models. If there are insufficient data within each center and treatment combination to allow estimation of effects, centers will be pooled based on similar surgical practices.

The adjusted least squares means will be estimated for each combination of time point and treatment. The treatment effect within each time point will be compared using a one sided test at the 5% level. Missing data will be excluded. The primary analysis will be performed for the ITT population.

The tests of the fixed effects will be presented, together with the estimated least squares means and summary statistics of the raw PaO2/FiO2 ratio for each of the two treatments at each time point. The estimated treatment difference between repertaxin and placebo at each time point will be presented together with the corresponding 95% confidence interval. The confidence interval will be generated using  $\alpha=0.10$  and the lower limit will be replaced by  $-\infty$ .

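### The 81%/56% power quoted for the 24 h comparison rests on the ICU-admission SD, without explanation, and on complete 24 h data, so it may be too low or too high depending on a missing share that the documents do not give

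*SAP*

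**What the plan says.** SAP 3.2 lists the inputs to the power statement. The comparison is "One primary comparison: repertaxin versus placebo at 24 hours post ICU admission", tested with "A one-sided two group t-test of statistical significance" at 0.05. The other inputs are "A placebo mean of 315 mmHg", "A common standard deviation of 137 mmHg" and "A sample size of 50 in each group". The result is 81% power for a 70 mmHg difference and 56% for 50 mmHg. The SAP attributes the mean and the SD to a database of 700 lung transplants and does not say which time point each belongs to.

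Protocol 9.1 gives the same power figures from the same inputs and reports the database by time point: "329±137 mmHg at the initial ICU assessment and 315±117 mmHg at 24 hours".

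Three other provisions decide how many patients have a 24 h value:
- **Measurement.** The ratio is taken during mechanical ventilation, and measurement stops at extubation (Protocol 4.2.1.1 and 7.5.2; SAP 3.1).
- **Analysis.** For the primary analysis SAP 9.5.1 says "Missing data will be excluded". Carrying the last value forward after early extubation, and scoring death as zero, belong to a sensitivity analysis.
- **Replacement.** Patients are replaced only if they received no study drug or no transplant (Protocol 7.10.2), not because a 24 h value is absent.

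**The concern.** The calculation combines the 24 h mean with the admission SD. For a fixed difference in mmHg the placebo mean does not affect power, so only the SD matters, and it is the SD that comes from the other time point. Used at 24 h, 137 understates power if the data are complete.

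The second assumption works the other way. Every extubation or death before 24 h takes the 24 h contrast below 50 per arm. The plan foresees such patients, since it has substitution rules for them, but the sample-size sections make no allowance for them.

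This is the trial's only power statement, and Protocol 9.1 uses it to discuss the risk of a Type II error. A reader of a null 24 h result would want to know what difference the comparison could have detected and how much missing data it could absorb. The present text answers neither question.

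**Working it through.** **Inputs.** Differences of 70 and 50 mmHg, one-sided alpha 0.05, 1:1 allocation and 50 per arm (SAP 3.2, Protocol 9.1 and 9.2). SD 137 at admission and 117 at 24 h (Protocol 9.1). The share of patients without a 24 h value is not in the documents, so 0% to 40% per arm is assumed as a range.

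**Formula.** For n evaluable per arm, SE = SD × √(2/n), df = 2n − 2 and noncentrality δ = difference / SE. Power is the probability that a noncentral t variable with that df and δ exceeds the one-sided 5% critical value of t.

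**Step 1: the plan's figure.** With SD 137 and n = 50, SE = 137 × √(2/50) = 27.4, df = 98 and the critical value is 1.661.
- 70 mmHg: δ = 70/27.4 = 2.555, power 81.4%.
- 50 mmHg: δ = 50/27.4 = 1.825, power 56.6%.

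These agree with the stated 81% and 56% to within a point. A two-sided test would give 71.6% and 43.9%, so the stated figures are one-sided, as described.

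**Step 2: the 24 h SD with complete data.** With SD 117 and n = 50, SE = 117 × √(2/50) = 23.4.
- 70 mmHg: δ = 70/23.4 = 2.991, power 90.8%.
- 50 mmHg: δ = 50/23.4 = 2.137, power 68.3%.

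The stated figures are about 10 and 12 points lower.

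**Step 3: the 24 h SD with missing values.**

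| Evaluable per arm | Missing | SE (mmHg), SD 117 | Power, 70 mmHg | Power, 50 mmHg |
|---|---|---|---|---|
| 50 | 0% | 23.40 | 90.8% | 68.3% |
| 45 | 10% | 24.67 | 87.9% | 64.3% |
| 40 | 20% | 26.16 | 84.3% | 59.9% |
| 36 | 28% | 27.58 | 80.8% | 56.0% |
| 35 | 30% | 27.97 | 79.8% | 55.0% |
| 30 | 40% | 30.21 | 74.1% | 49.6% |

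**Step 4: where the two assumptions cancel.** The SEs are equal when n = 50 × (117/137)² = 36.5. At 36 per arm (14/50 = 28% missing), power rounds to the plan's own 81% and 56%. At 37 per arm (26% missing) it is 81.7% and 57.0%.

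**The case against.** The strongest reply is that 137 was chosen on purpose. The primary endpoint has two time points, and Protocol 9.1 says the size was based on both. Taking the larger SD gives one figure that is exact for admission with complete data and conservative at 24 h with complete data. It also absorbs missing 24 h values up to a little over a quarter. That reading is plausible and the documents do not rule it out. They do not state it either, and SAP 3.2 presents 137 as an assumption for a comparison it places at 24 h. One sentence in the plan would settle this part.

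Other parts of the reply also stand:
- There is no arithmetic error; the stated power follows from its inputs.
- The SD is not hidden. Protocol 9.1 prints both values and says that 137 was used, and the SAP is to be read with the protocol. What is missing is the reason.
- The planned analysis is a center-adjusted repeated-measures model. It can keep the admission values of patients who lack a 24 h value and so recover part of the lost information. The documents give no within-patient correlation from which to quantify this, so the table approximates that model's power.
- Protocol 9.1 already treats power as uncertain, because no data on effect size were available.

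A reader might infer that the trial is underpowered at 24 h. The documents do not support that. With their own 24 h SD, power for 70 mmHg runs from 91% to 74% over the assumed range, on both sides of 81%, and the missing share is unknown.

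**Conclusion.** The concern holds as a misstated and incompletely explained power figure. Under the database's 24 h SD, 81%/56% is the power of the named comparison only if about 28% of 24 h values are missing. With complete data it is too low by about 10 points (70 mmHg) and 12 points (50 mmHg). At 40% missing it is too high by about 7 points (81.4 − 74.1 for 70 mmHg; 56.6 − 49.6 for 50 mmHg). The direction for this trial cannot be determined from the documents.

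The SD mismatch and the lack of any allowance for missing values are certain from the text. The sizes rest on a complete-case two-group t-test, equal missingness in both arms, the assumed 0% to 40% range, and a 24 h SD of 117 carrying over to the trial patients who have a value. No estimate, test or decision rule in the plan is affected.

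**What to change.** Keep n = 100 and revise SAP 3.2 and Protocol 9.1 as follows:

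1. State 24 h power with SD 117 over a named range of evaluable patients per arm, for example 50, 45, 40, 36 and 30, using the table above. Give the expected share without a 24 h value and its source, or say that it is unknown.
2. Either keep 81%/56% as the ICU-admission figure (SD 137, 50 per arm), or state that 137 is a deliberately conservative choice for both time points and that at 24 h it covers about 28% missing.
3. Note that these are complete-case t-test approximations to the center-adjusted repeated-measures model in SAP 9.5.1.

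The cost is wording only. Recruitment, conduct and analysis do not change. The SAP is to be finalized before database lock, so the text can still be corrected there, with an entry in SAP 1.2 if the protocol wording is left for a later amendment.

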### 3.3 Randomization

Prior to surgery, patients who meet all the entry criteria and who provide written informed consent will be randomized to receive either repertaxin or placebo according to a 1:1 randomization.

A master randomization list was prepared for 352 patients (44 at each of 8 centers) by Insight Statistical Consulting on behalf of PPD. A dummy randomization was reviewed by statisticians at both PPD and Dompé prior to production of the final version. Since each patient should only ever require a single drug pack, the randomization number is identical to the patient number.

The randomization number is assigned sequentially at each site as patients are found to be eligible for entry to the study and are enrolled. Patients who are enrolled to replace patients who withdraw from the study prior to study drug infusion or lung transplantation will be issued a new randomization/patient number.

If a patient is allocated a randomization number and either the transplant does not happen or the study drug is not administered, the relevant drug box should be annulled to avoid its re-use with another patient.

## 4 STUDY VARIABLES AND COVARIATES

### 4.1 Primary variable

The primary variable within the study is  $\text{PaO}_2/\text{FiO}_2$  ratio measured at ICU admission (time 0) and 24 hours post ICU admission.

### 4.2 Secondary variables

#### 4.2.1 Efficacy

- Time profile of  $\text{PaO}_2/\text{FiO}_2$  ratio measured ICU admission and at 24, 48 and 72 hours post ICU admission or until extubated whichever occurs earlier.
- PGD score
- Time to freedom from mechanical ventilation
- Duration of ICU stay
- ICU mortality
- Mortality in the first 30 days post-transplant
- FEV1 and FVC at Months 1, 6 and 12 post-transplant
- BOS score at Months 6 and 12 post-transplant
- Cumulative acute rejection episodes at months 6 and 12 post-transplant
- Patient survival rate evaluated at Months 6 and 12 post-transplant

#### 4.2.2 Safety

- Study drug dosing
- Incidence of adverse events
- Incidence of clinically significant results and shifts (relative to normal ranges) in hematology, clinical chemistry and coagulation test results
- Incidence of concomitant medication use
- Vital signs
- Cardiopulmonary measurements

#### 4.3 Predetermined Covariates and Prognostic Factors

- Type of transplant (single or double)

Data recorded only at Months 6 and 12 will not be covered within this document but will be discussed in the Month 12 SAP.

Data for PMN count in bronchoalveolar lavage (BAL) and plasma levels of repertaxin and its major metabolite DF2243Y will not be analyzed PPD. These data will be provided in separate stand alone reports by the responsible laboratories. These reports will be included as appendices to the CSR.

## 5 DEFINITIONS

### Time 0

This is defined as date and time of ICU admission.

### Month 1

This is defined as 30-35 days after date of lung transplant.

### Month 6

This is defined as 24 – 28 weeks (166 – 196 days) after date of lung transplant.

### Month 12

This is defined as 50 – 54 weeks (350 – 378 days) after date of lung transplant.

### Age

The integer age of the patient will be derived relative to the date of the screening visit using the following SAS code:

```
age = INTCK('YEAR', dob, dos) - ((MONTH(dos) < MONTH(dob)) OR  
(MONTH(dos) = MONTH(dob) AND DAY(dos) < DAY(dob)));
```

where dob = date of birth and dos = date of screening visit.

### Transplant type

This is defined as either single or double where a single transplant is defined as a single left lung or a single right lung and a double transplant is defined as a bilateral sequential lung or an en-bloc double lung.

### Duration of cold ischemia

This is the interval in hours between onset of organ ischemic time (date and time of cross-clamp on donor organ) and the removal of the donor organ from cold storage and is derived as:  
(Date/time of organ removal from cold storage – date/time of cross clamp on donor organ)/3600

### Duration of warm ischemia

This is the interval in hours between removal of donor organ from cold storage and the start of reperfusion or vascular de-clamping of the allograft and is derived as:  
(Date/time of start of reperfusion – date/time of organ removal from cold storage)/3600

### Duration of cold and warm ischemia

This is the interval in hours between onset of organ ischemic time and the start of reperfusion and is derived as:  
(Date/time of start of reperfusion – date/time of cross clamp on donor organ)/3600

